Using post PCI FFR to guide stent optimisation and/or further intervention in the target vessel has been shown to increase the frequency of achieving optimal post PCI FFR results (and therefore presumably better clinical outcomes). However, there are additional costs involved in the routine use of post PCI FFR and it is not clear just how often it is even possible to increase the initial post PCI FFR to ≥ 0.90 . This uncertainty means that it is currently difficult to either recommend the routine use of post PCI FFR or justify its cost. We propose a prospective study to assess the feasibility of achieving post PCI FFR ≥ 0.90 during standard PCI procedures in consecutive patients. We would also attempt to elucidate the mechanisms for sub-optimal FFR results when they occur. We would anticipate using the data from this developmental study to support a subsequent funding application to BHF/MRC/NIHR for a definitive phase 3 study of the impact of FFR targeted PCI on clinical outcomes.

Background

The utility of FFR for assessing the physiological significance of coronary stenoses and the benefits of FFR-guided decision making prior to PCI have been well established in several landmark trials.^{1,2} There is also a growing body of evidence that post PCI FFR can predict clinical outcomes. Much of this data is from the era of bare-metal stents, when a post-stent FFR ≥ 0.95 was recommended as the cut-off value for optimum (physiologically guided) stent implantation. This value was validated in a series of intravascular ultrasound (IVUS) studies although it should be noted that most studies of IVUS guided stenting have shown little or no benefit in terms of longer term clinical outcomes.³⁻⁶

More recent studies on the prognostic value of FFR post drug-eluting stent (DES) implantation have suggested that a post PCI FFR of ≤ 0.90 correlated with greater adverse cardiac event rates.⁷⁻¹² However, these series have generally recruited small numbers of patients and have yielded conflicting results. For example, Leesar et al investigated a group of 66 patients undergoing PCI with primarily DES. They found that an FFR ≥ 0.96 was achieved in only 35 patients (53%) after PCI but adverse event rates were significantly lower in this group.⁷ Conversely, Matsuo et al reported that a post-stent FFR of ≥ 0.90 was achieved in only 39% of their cohort of 69 patients and were unable to demonstrate that post-stent FFR predicted target lesion revascularisation (TLR) in patients who received DES.⁸ A larger, retrospective study of 664 lesions (in 574 patients) by Agarwal et al found that approximately 1 in 5 lesions (21%) demonstrated persistent ischaemia (post PCI FFR ≤ 0.81) after intervention despite angiographically satisfactory PCI results.¹³ The authors report that a post PCI FFR of > 0.91 was achieved in 34% of their patients which increased to 43%

following subsequent interventions to achieve “functional optimization”. After excluding patients with diabetes, CKD and/or diffuse coronary disease, achieving a final FFR > 0.91 was associated with lower adverse event rates compared to the final FFR ≤ 0.91 group (7.1% vs. 18.9%; $p = 0.04$).

Data from a small series of patients at our own institute would also appear to corroborate the previous findings that an initial post PCI FFR ≥ 0.90 is only achieved in less than 40% of patients. Of the 21 patients in this group, only 8 (38%) had an initial post PCI FFR ≥ 0.90 . Following further stent optimisation and/or additional stenting, this increased to 12 patients (57%) with a final FFR ≥ 0.90 .

Pijls et al measured post PCI FFR in 750 patients and reported a final FFR result > 0.90 in 68% of their cohort. They found that FFR after stenting is a strong independent predictor of outcome at 6 months and that the event rate was over three times higher in patients with post PCI FFR < 0.90 compared to those with an FFR between 0.90 and 0.95 (20.3% vs. 6.2%).¹⁴

In a meta-analysis from Johnson et al, almost 2/3 of 966 patients who had post PCI FFR measured had values below 0.90. The rate of MACE (death, MI, repeat revascularisation) was 40% at 3 years in patients within the lowest tertile of post PCI FFR [median IQR 0.83 (0.79-0.86)], almost twice as high as that in patients in the highest tertile of post PCI FFR [0.98 (0.96-1.00)]; $p < 0.001$.¹⁵ This may of course reflect the effects of diffuse atherosclerosis but it may also indicate physiologically suboptimal revascularisation and thereby represents a target for improved treatment.

Rimac et al recently published one of the largest meta-analyses to date on the clinical value of post PCI FFR. They included a total of 105 studies from 1995 - 2015 (7470 patients) and found that higher post PCI FFR values (≥ 0.90) were associated with reduced rates of repeat intervention and MACE. They concluded that FFR measurement after PCI was associated with prognostic significance and recommended further investigation to assess the role of post PCI FFR and validate cut off values in contemporary clinical practice.¹⁶

Original hypothesis

A simple Physiologically-guided Incremental Optimisation Strategy (PIOS) can increase the proportion of patients undergoing PCI in whom a post PCI FFR ≥ 0.90 can be achieved from 40% to 60%.

Experimental details and design of proposed investigation

Overall aim:

A randomised control trial of a physiologically-guided optimisation strategy to determine the feasibility of increasing the proportion of post PCI FFR measurements ≥ 0.90 in a consecutive series of patients undergoing standard PCI procedures.

Study Population:

260 consecutive patients with stable angina referred for invasive management to the cardiac catheterisation lab who have been selected to undergo PCI based on either angiographic appearances or prior FFR assessment. Patients will be caffeine free for >12 hours pre-procedure.

Inclusion criteria:

Patients >18 years of age with coronary artery disease including stable angina and stabilised non-ST-elevation myocardial infarction (NSTEMI) able to provide informed consent.

Exclusion Criteria:

- PCI in a coronary artery bypass graft
- Inability to receive adenosine (for example, severe reactive airway disease, marked hypotension, or advanced atrioventricular block without pacemaker).
- Recent (within 1 week prior to cardiac catheterization) ST-segment elevation myocardial infarction (STEMI) in any arterial distribution (not specifically target lesion).
- Severe cardiomyopathy (ejection fraction <30%).
- Renal insufficiency such that an additional 20 to 30 mL of contrast would, in the opinion of the operator, pose unwarranted risk to the patient.

Methods/Design:

Informed consent will be obtained prior to cardiac catheterisation in all potential subjects conforming to the inclusion and exclusion criteria.

Patients will then be randomised to one of two groups (described below) and PCI will be performed, using a pressure guidewire, according to standard practice at the Golden Jubilee National Hospital (including lesion pre-dilation and post-dilation of the stented segment).

Group 1 (PIOS Group):

Operator-blinded FFR will be measured post PCI.

If FFR is ≥ 0.90 , no further intervention will be performed and the procedure is considered complete.

If FFR is < 0.90 , the result will be disclosed to the operator and a hyperaemic pressure wire pullback during either a standard peripheral intravenous adenosine infusion (140mcg/kg/min) or an intracoronary adenosine infusion (360mcg/min) via a microcatheter will be performed. Depending on the result the operator would then have the following options:

- A. If there is a step-up of ≥ 0.05 across the stented segment(s) further post-dilatation with a 0.25 - 0.50mm larger non-compliant balloon to at least 18 atmospheres should be performed followed by repeat FFR. Alternatively, the operator may choose to employ intracoronary imaging (IVUS or OCT) to guide post-dilation/optimisation of the stented segment.

- B. If there is a step-up of ≥ 0.05 across a relatively focal (<20mm) unstented segment which is technically suitable for further stenting then a further stent should be implanted followed by repeat FFR.
- C. If the FFR remains < 0.90 after steps A +/- B, a further FFR pullback will be performed. If the criteria for Step B are again met, one additional stent may be deployed and a final FFR pullback performed. Following this, the FFR result will be accepted.
- D. If the residual pressure gradient is interpreted to reflect diffuse atherosclerosis with no focal step-ups, the result is accepted.
- E. At the end of the procedure the pressure wire sensor will be withdrawn to the tip of the guiding catheter and compared with the aortic pressure. A pressure drift of ≤ 0.03 will be accepted and the final FFR result adjusted accordingly.
- F. If there is a drift of ≥ 0.04 , the wire should be re-equalised and the final FFR measurement be repeated.
- G. The patients will have their demographics and procedure details recorded. All patients will receive 3-month telephone follow-up.

Group 2 (Control Group):

Post PCI FFR will be recorded but not disclosed to the operator. The angiographically defined result will be accepted. The patients will have their demographics and procedure details recorded. All patients will receive 3-month telephone follow-up.

Primary Outcome

The primary end-point in this study will be the proportion of patients with a physiologically optimal result post PCI (FFR ≥ 0.90). We hypothesise that our PIOS intervention can increase the proportion of patients achieving this target from 40% to 60% and believe that an increment of at least this magnitude would be necessary to make a future larger study with both patient-oriented clinical (target vessel failure) and health care system (resource utilisation) outcomes acceptable to the interventional cardiology community and potential funders.

Secondary Outcomes

The main secondary outcome measure will centre on assessing change from baseline in self-reported health outcomes at 3 months using both generic and disease-specific quality of life measurement tools.

The EQ5D is a generic quality of life measurement tool which expresses preference for health status using a single index score and is the recommended tool by the National Institute for Health and Clinical Excellence (NICE) for calculation of Quality-Adjusted Life Years. It covers 5 dimensions of health: mobility, self-care, usual activities, pain/discomfort, and anxiety/depression.

The SAQ is a self-administered, disease-specific measure for patients with coronary artery disease that has previously been demonstrated to be valid, reproducible, and sensitive to

clinical change. The SAQ quantifies patients' physical limitations caused by angina, the frequency of and recent changes in their symptoms, their satisfaction with treatment, and the degree to which they perceive their disease to affect their quality of life.

The rate of target vessel failure and its component features (cardiac death, myocardial infarction, stent thrombosis, unplanned rehospitalisation with target vessel revascularisation) will be analysed at 3 months.

Additional secondary outcomes including procedural/patient safety factors will also be measured. These would include: procedure time, fluoroscopy dose, contrast dose, complications and cost of additional equipment employed (balloons/stents/intra-coronary imaging).

Power calculations

Assuming (as per data from previous studies) that 40% of patients in the control arm have a post PCI FFR ≥ 0.90 and that it is considered clinically relevant if the equivalent percentage in the PIOS treatment arm is at least 60%, we will require a sample size of 130 per group to have 90% power to be able to detect a difference in the population in these proportions at the 5% significance level.

Expected value of results

1. Confirmation that the proposed PIOS protocol significantly increases the proportion of patients obtaining a physiologically optimal post PCI result will demonstrate the feasibility of this strategy and should lead to an increase in post PCI pressure wire usage to achieve physiologically optimal results for patients.
2. The secondary outcome measures, albeit underpowered for clinical outcomes in this study, will hopefully still give a signal that achieving a target post PCI FFR ≥ 0.90 does yield objective benefits for patients. This could then form the basis for a larger phase 3 trial to confirm improved clinical outcomes and cost-effectiveness of FFR targeted PCI

References

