1.3 Study Design

A single centre, parallel group, randomised controlled clinical trial. Patients are randomised in a 1:1 ratio to receive either a physiology-guided optimisation strategy (potentially undergoing additional stent post-dilation and/or further stenting in the target vessel as appropriate) or standard care. The framework for the trial is testing the superiority of the extra treatment in terms of its efficacy.

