1.4 Randomisation

Randomisation will be performed using a 1:1 variable block (2,4,6) randomisation method generated from within the study's electronic Case Report Form (eCRF) platform, Castor EDC.

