1.5 Blinding

Patients will not be informed of their final coronary physiology results. FFR results will not be displayed on the procedure-room monitor and the physiology interface will only be visible to research staff in the control room. These results will only be disclosed to the operator for patients with initial post-PCI FFR <0.90 who are randomized to receive the optimisation strategy. The rationale for maintaining operator-blinding for all other post-PCI physiology results is to try and minimise the potential Hawthorne effect ('observer effect') the study could have on local PCI practices.

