2.2 Baseline Characteristics

Baseline characteristics will be summarised in the FAS as a whole and by treatment group. The following baseline characteristics will be reported:

- Demographics: age (years), sex (male, female), height, weight, BMI, ethnicity (White or White British, Asian or Asian British: South Asian, Asian or Asian British: Chinese, Asian or Asian British: Other Asian, Black or Black British, Mixed or Multiple, Other)
- Lifestyle Factors: Smoking Status (No, Current, Ex-Smoker <12 months, Ex-Smoker >12 months)
- Vital Sign Observations: heart rate, blood pressure
- Pharmaceutical therapy (medications used for treatment of cardiovascular disorders including primary and secondary therapies)
 - Number of antianginal medications
- Medical History including Risk Factors (yes/no unless otherwise stated)
 - Indication for Angiogram (Stable Angina, ACS-NSTEMI, ACS-Unstable Angina)
 - Time since NSTEMI
 - Troponin Assay Used and Peak Troponin Recorded if NSTEMI
 - Hypertension
 - Hypercholesterolaemia
 - Diabetes
 - TIA/Stroke
 - CKD
 - Thyroid Dysfunction
 - Pacemaker
 - ICD
 - Atrial Fibrillation
 - Heart Failure (No, HF-rEF, HF-pEF)
 - NYHA Class if Heart Failure (1-4)
 - Previous PCI
 - Previous MI
 - History of Previous MI in Target Vessel if Yes
 - CABG
 - Angina
 - Canadian Cardiovascular Society (CCS) Class if Angina (1-4)
 - Valvular Heart Disease
 - Valve Replacement/Repair
 - Family History of CAD
- Health Status questionnaire scores:
 - Seattle Angina Questionnaire
 - EQ-5D-5L
- Procedural Characteristics
 - Vascular Access (Radial, Femoral, Brachial)
 - Sheath Size

- Multivessel Procedure (Yes, No)
- Procedure Time
- Duration of Research Protocol
- Contrast Dose
- Dose Area Product
- Radiation Dose
- Total Duration of Adenosine Infusion
- Total Dose of Adenosine
- Total Number of Stents Deployed in Study Artery
- Total Length of Stents Used in Study Artery
- Diameter of Largest Balloon used for PCI
- Largest Stent Diameter

- Angiographic Characteristics
 - Target Coronary Artery Segment
 - Lesion Severity by Operator's Visual Assessment (Normal, Plaque Disease, <25%, 25-49%, 50-74%, 75-94%, >/= 95%, Subtotal Occlusion, Occluded)
 - AHA Lesion Type
 - Lesion APPROACH Score
 - Gensini Score
 - QCA Lesion Length
 - Pre- and Post-PCI QCA Diameter Stenosis
 - Pre- and Post-PCI QCA Area Stenosis
- Pre- and Post-PCI Coronary Physiology Test Results
 - Ratio of distal coronary to aortic pressure (Pd/Pa)
 - Diastolic Pressure Ratio (dPR)

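### Patients are randomised before the index PCI and nothing withholds the arm from the operator, who could know it during the PCI that sets the first FFR and, in PIOS, read silence as FFR ≥0.90

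*Protocol*

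**What the plan says.** **Order of events.** Protocol Methods/Design places allocation after consent and before treatment: "Patients will then be randomised to one of two groups (described below) and PCI will be performed, using a pressure guidewire". The index PCI follows the hospital's standard practice in both arms, including pre-dilation and post-dilation. Balloon size and stent length are not fixed.

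**Randomisation.** SAP 1.4 gives the method and platform: "Randomisation will be performed using a 1:1 variable block (2,4,6) randomisation method generated from within" the eCRF. It does not say when in the procedure allocation is generated, or who sees it.

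**Blinding.** Every provision concerns FFR values.
- Protocol, Group 1: the first post-PCI FFR is measured with the operator blinded. At ≥0.90 the procedure ends; below 0.90 the value is disclosed and the optimisation steps begin.
- Protocol, Group 2: "Post PCI FFR will be recorded but not disclosed to the operator".
- SAP 1.5: "the physiology interface will only be visible to research staff in the control room", and "These results will only be disclosed to the operator for patients with initial post-PCI FFR <0.90 who are randomized to receive the optimisation strategy". The reason given is: "The rationale for maintaining operator-blinding for all other post-PCI physiology results is to try and minimise the potential Hawthorne effect".

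**Effect under test.** SAP 1.3: "The framework for the trial is testing the superiority of the extra treatment in terms of its efficacy".

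**Reporting.** SAP 2.2 lists "Pre- and Post-PCI Coronary Physiology Test Results" by group and includes FFR, without labelling the post-PCI value as initial or final; only the yes/no items refer to the final value. Its stent and balloon items are totals or maxima for the whole procedure. SAP 2.4 names blinding integrity as a feasibility outcome without a measure.

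**The concern.** An operator who knows the arm during the index PCI may work differently in the two arms. In PIOS, they may do more because the result will be tested, or less because a second attempt is available. In controls, they may do more because the angiographic result is final. The documents do not indicate which.

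Any such difference acts before the first FFR. The extra treatment that SAP 1.3 sets out to test starts only after it. A difference in the index PCI is not that effect, but it would enter the primary comparison together with it.

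The second problem is logical and needs no assumption about behaviour. Every PIOS value below 0.90 is disclosed. If the operator knows the patient is in PIOS, silence therefore means FFR ≥0.90. The SAP 1.5 rule protects PIOS results ≥0.90 only if the arm is hidden, and neither document says that it is. Operators would receive the feedback that SAP 1.5 withholds in order to limit a Hawthorne effect on local practice.

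**Working it through.** **Inputs.** 130 per arm, 40% versus 60%, 90% power, 5% level (Protocol, Power calculations; SAP 1.6). Two-sided tests (SAP section 2). Adjusted Wald and Fisher's exact test (SAP 2.3.1). Pilot first-FFR rate 16/50 = 32% (SAP 1.6).

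**1. The plan's own figure.** With pooled variance and no continuity correction:

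n = [1.96·√(2·0.5·0.5) + 1.2816·√(0.4·0.6 + 0.6·0.4)]² / 0.20² = 129.3, so 130 per arm (power 90.2%). The stated sample size reproduces.

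**2. Patients whose endpoint is the first FFR.** These are all controls, plus PIOS patients already at ≥0.90.
- At 40%: 130 + 0.40·130 = 182; 182/260 = 70%.
- At 32%: 130 + 0.32·130 = 171.6; 171.6/260 = 66%.

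**3. What silence reveals.** SAP 1.5 intends disclosure in 130 − 52 = 78 patients (30%).
- Arm known: the operator learns whether FFR is ≥0.90 in all 130 PIOS patients (50%), including the 52 meant to stay blinded.
- Arm withheld, and revealed only for PIOS <0.90: silence means control or PIOS ≥0.90. Then P(FFR ≥0.90 | silence) = (52 + 52)/(130 + 52) = 104/182 = 57%, against a prior of 40%. At the pilot rate it is 83.2/171.6 = 48%, against 32%.

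**4. Illustration of a shift in first-FFR success.** The documents give no size, so 2 and 5 points are assumptions. Rates are exact binomial enumerations at 130 per arm; adjusted Wald adds one success and one failure per arm.

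No PIOS effect:

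| True rates | Adjusted Wald | Fisher |
|---|---|---|
| 40% v 40% | 5.0% | 3.7% |
| 42% v 40% | 6.3% | 4.8% |
| 45% v 40% | 13.2% | 10.6% |

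Planned effect, modelled as one third of PIOS patients below 0.90 converting (0.40 + 0.60/3 = 0.60), with an unfavourable shift:

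| Shift | Final rates | Difference (points) | Power, adjusted Wald | Power, Fisher |
|---|---|---|---|---|
| None | 60% v 40% | 20 | 90.8% | 88.5% |
| PIOS −2 | 58.7% v 40% | 18.7 | 86.6% | 83.7% |
| Controls +2 | 60% v 42% | 18 | 84.1% | 80.8% |
| PIOS −5 | 56.7% v 40% | 16.7 | 78.2% | 74.3% |
| Controls +5 | 60% v 45% | 15 | 69.3% | 64.8% |

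Favourable 5-point shifts give 0.45 + 0.55/3 − 0.40 = 23.3 points (PIOS +5) or 25 points (controls −5). The range of 15 to 25 points comes from shifting controls; shifting PIOS gives 16.7 to 23.3.

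**5. Can a later check replace prevention?** For first FFR ≥0.90 by arm, SE = √(2·0.24/130) = 0.0608, so the 95% CI is ±1.96·0.0608 = ±11.9 points. Power to detect a 5-point shift is 13%. The check cannot exclude a shift of that size.

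**The case against.** **This is silence, not a demonstrated flaw.** The operator-blinding provisions make most sense if the arm is also hidden until disclosure, and operators may already be kept unaware. That is possible, and the point claims only that they could know. But followed as written, the protocol permits early knowledge. If practice already withholds the arm, the remedy is to write that down.

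**This is a strategy trial.** The SAP 1.2 hypotheses compare an optimisation strategy with standard care, so changed behaviour might count as part of the strategy. However, SAP 1.3 names the extra treatment as what is tested, and the protocol prescribes the same index PCI in both arms. A difference arising there is not intended.

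**The illustrated shifts have no source.** This stands. The no-effect scenario also sits poorly with the gains reported in the protocol's Background (34% to 43% in the large series; 8 to 12 of 21 patients locally). The PIOS −2 and −5 rows assume that patients pushed below 0.90 convert at the same one-third rate. If optimisation recovers all of them, the final rate stays at 60% and power at 90.8%. The tables show sensitivity; they do not estimate bias.

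**The fix may leak.** Drift steps E and F appear only under Group 1 in the protocol. If the drift check were done in PIOS patients at ≥0.90 but not in controls, it could reveal the arm. The text can be read otherwise: those steps sit in the list that follows the <0.90 branch, and SAP 2.2 lists drift for the whole FAS. Any leak would come after the first FFR, so the main protection holds, but the passages should be reconciled.

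**Conclusion.** The concern holds, as a change that should be made. Randomisation precedes the index PCI and no provision withholds the arm from the operator. This leaves an avoidable route for performance bias in the procedure that sets the endpoint for about 70% of patients (66% at the pilot rate). If the arm is known, it also defeats the SAP 1.5 blinding of PIOS results ≥0.90: silence identifies them with certainty, against 57% (48% at the pilot rate) if the arm is withheld as proposed.

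The direction and size of any bias are unknown, and whether operators are in fact told the arm cannot be settled from the documents, so confidence is medium. The case rests on the order of events and the logic of the disclosure rule, and on the low cost of closing the gap. It does not depend on the assumed 2- or 5-point shifts.

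**What to change.** **Protocol Methods/Design and SAP 1.4/1.5.** Add: *The arm is not revealed to the operator until the index PCI is declared complete and the blinded first FFR is stored; after that it is revealed only for PIOS patients with a first FFR below 0.90.* Control-room research staff, who alone see the physiology interface, can hold the allocation. Alternatively, the eCRF can randomise only once the first FFR is saved, with the same reveal rule. State also whether the drift check applies to both arms.

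**SAP 2.2.** Label post-PCI FFR as initial or final. Report initial FFR by arm, as a value and as ≥0.90 yes/no. Record stent and balloon data at the end of the index PCI, since the present totals and maxima include later optimisation in PIOS.

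**SAP 2.4.** Define blinding integrity to include any early reveal of the arm or of FFR, counted by arm.

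**Cost.** Wording, a control-room rule or a change in eCRF form order, and a short mid-procedure step. No extra patients or measurements are needed; sample size, primary test and clinical steps are unchanged. Withholding the arm leaves the FAS and randomisation scheme as they are. Moving randomisation itself narrows the FAS: patients with failed PCI or unmeasurable FFR would not be randomised and should be counted in the screening log. If enrolment has begun (protocol dated 08 June 2017, SAP 23/07/2019), the change is prospective only, and initial FFR by arm should be reported before and after it.
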